### 7.5.2 Adverse Events

Adverse events will be collected and coded using the current version of the Medical Dictionary for Regulatory Activities (MedDRA v18.1).

An adverse event is considered treatment-emergent if the date of onset is on or after the date of first stimulation in the randomized period, or worsened during the randomized or open-label periods (intensity and/or severity changed to a worse grade).

**Events with Irregular Start Dates:** All adverse events will be included in the tabulations regardless the completeness of the onset dates. Partial dates may be imputed when appropriate.

If a partial date is reported for the start of an adverse event, a complete date will be estimated by the following algorithm in order to determine treatment emergent:

1. If month and day are missing: The year of the event will be compared to the year in which study treatment began. If the two years are not the same, then January 1 will be used. If the two years are the same, then the earlier of the date of randomization and the date of first usage of the device will be used.
2. If day is missing: The month and year of the event will be compared to the date in which study treatment began. The onset date will be imputed as the date closest to (being either on or after) the earlier of the date of randomization and the first date of usage of the device. If the two did not occur in the same month and year, then 1 will be used for the day.

If a partial date is reported for the end of an adverse event and the adverse event is not continuing, a complete date will be estimated by the following algorithm:

1. If month and day are missing: The year of the event will be compared to the year of final contact with the subject. If the two years are not the same, then December 31 will be used. If the two years are the same, then the date of final contact with the subject will be used.
2. If day is missing: The year of the event will be compared to the year of final subject contact. If the two years are not the same, then the last day of the month will be used for the day. If the two years are the same, then the month of the event will be compared to the month of final subject contact. If the months are not the same, then the last day of the month will be used for the day. If the two months are the same, then the date of final subject contact will be used.

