## 3. STUDY DESIGN

### 3.1 Study Design

This is a prospective, randomized, sham-controlled, multi-center investigation designed for comparison of two parallel groups, gammaCore®-R (active treatment) and a sham (inactive) treatment. The study period will begin with a four week run-in period, during which there is no investigational treatment. The purpose of the run-in period will be to establish the baseline for comparisons. The run-in period will be followed by a 12 week randomized period when the subjects will be randomized (1:1) to either active treatment or sham (inactive) treatment. Figure 1 graphically displays the study design.

The randomized period will be followed by a 24 week open label period, where the subjects in the sham treatment group will switch treatment assignment and receive a gammaCore®-R device and the gammaCore®-R group will continue to receive an active treatment (See Protocol Section 7.1 for details).

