**Table 2. Clinical Investigation Flow Chart**

Period	Run-in	Randomized					Open label					
Visit number	V1	V2	V3*	V4	V5 **	V6	V7 *	V8	V9**	V10	V11	V12
Week	-4	0	1	4	8	12	13	16	20	24	30	36
Day	-28	1+/-3	7+/-3	28+/-3	56 +/- 5	84 +/-5	91 +/-3	112 +/- 3	140+/-5	168+/-5	210 +/-5	252+/-5
Signed Consent Form	✓											
Randomization		✓										
Demographics	✓											
Inclusion/Exclusion criteria	✓											
History of migraine	✓											
Medical and surgical history	✓											
Physical examination	✓											
ECG	✓											
Urine pregnancy test 	✓											
Blood pressure and weight	✓					✓						✓
HIT-6 		✓		✓	✓	✓	✓	✓	✓	✓		✓
EQ-5D-5L 		✓		✓	✓	✓	✓	✓	✓	✓		✓
MIDAS 		✓				✓				✓		✓
Subject satisfaction question						✓						✓
Easy to use question						✓						✓
Blinding question			✓			✓						
Device training and placement		✓		✓		✓						
Collect device/ gammaCore®-R						✓						✓
Diary completion	✓	✓	✓	✓	✓	✓	✓	✓	✓	✓	✓	✓
Concomitant medication	✓	✓	✓	✓	✓	✓	✓	✓	✓	✓	✓	✓
Adverse Event 		✓	✓	✓	✓	✓	✓	✓	✓	✓	✓	✓
Study Termination												✓

 Fertile woman only.

 All new events during the run-in will be reported under adverse events.

Call\* - One week after the previous visit.

Call \*\*- One month after the previous visit.

 At visit 2 and 6 these questionnaires will be completed by the subjects on paper forms during the visit.

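### The partial-onset rules for adverse events ignore the stop date, so a run-in event known to have ended before treatment can be dated after its own resolution and counted as double-blind

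*SAP*

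**What the plan says.** SAP section 7.5.2 defines treatment emergence by onset: "An adverse event is considered treatment-emergent if the date of onset is on or after the date of first stimulation in the randomized period". Worsening during the randomized or open-label period also qualifies. For an incomplete start date, "a complete date will be estimated by the following algorithm in order to determine treatment emergent". The algorithm has two rules:

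- **Rule 1, month and day missing.** If the year is that of treatment start, "then the earlier of the date of randomization and the date of first usage of the device will be used". Otherwise 1 January is used.
- **Rule 2, day missing.** If month and year are those of treatment start, "The onset date will be imputed as the date closest to (being either on or after) the earlier of the date of randomization" and first device use. Otherwise: "If the two did not occur in the same month and year, then 1 will be used for the day".

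The separate rules for incomplete stop dates compare only with the date of final contact.

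Pre-treatment events reach these rules. Section 3.1 states: "The study period will begin with a four week run-in period, during which there is no investigational treatment". A footnote to Table 2 adds: "All new events during the run-in will be reported under adverse events". Section 8.5.2 tabulates events for the double-blind and open-label phases and lists no run-in phase.

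**The concern.** Moving an unknown onset to treatment start is a sound conservative default when nothing contradicts it. Here it is applied even when the record does contradict it. If the stop date lies before treatment, the onset must also lie before treatment, yet the rule places it at randomization.

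This has two consequences. The analysis data hold events that begin after they end. Events that the device cannot have caused also move from outside the phase tables into the double-blind counts. Adverse events are among the secondary objectives in section 2.2, so the absolute rates matter to readers.

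**Working it through.** The SAP gives no figure to reproduce, so the check applies its rules to dates.

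**Inputs.** The run-in is 28 days (sections 3.1 and 6.2). The rules and the definition are those of section 7.5.2. Table 2 ticks both randomization and "Device training and placement" at V2. Same-day first use is an inference from that, as is assignment to a phase by imputed onset date. The even spread of dates is an assumption.

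**Worked example.** Randomization and first use are on 21 March 2016. A run-in event is recorded as starting in March 2016 (day unknown) or in 2016 (month and day unknown), and it stopped on 5 March 2016.
- Imputed onset under either rule: 21 March.
- Gap after resolution: 21 − 5 = 16 days.
- Treatment-emergent: yes, since 21 March is on or after first stimulation.

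If first use is instead on 22 March, rule 1 still gives 21 March. The onset is still after resolution, but it now precedes first stimulation, so the event is not treatment-emergent.

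**Share affected, same-day first use.** An onset k days before randomization falls in the same calendar month with probability of about 1 − k/30.4, and in the same year with probability of about 1 − k/365.25. Both are linear in k, so only the mean of k matters.

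| Weighting | Mean k | Day missing | Month and day missing |
|---|---|---|---|
| Each onset day 1–28 equally | 14.5 | 1 − 14.5/30.4 = 0.52 | 1 − 14.5/365.25 = 0.96 |
| Each onset–stop pair equally, stop by day −1 | 7714/406 = 19 | 1 − 19/30.4 = 0.375 | 1 − 19/365.25 = 0.948 |

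In the second row an onset on day −k has k possible stop days, so the mean is Σk²/Σk.

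**Enumeration.** This took every randomization date in 2016, every onset from day −28 to day −1, and every stop date from onset to day −1, which gives 366 × 406 = 148,596 combinations. Rule 2 was read as giving the reference date itself.

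| First use after randomization | Onset after stop: day missing | Onset after stop: month and day missing | Treatment-emergent |
|---|---|---|---|
| Same day | 37.7% | 94.8% | the same 37.7% and 94.8% |
| 1 day | 34.4% | 94.5% | 0% |
| 3 days | 28.0% | 94.0% | 0% |

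In the remaining combinations the month or year differs from that of treatment start, and the rule gives the first of the month or 1 January. Neither error then arises.

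**The opposite error.** Take randomization on 21 March, first use on 22 March, and a true onset on 2 May with month and day missing. Rule 1 gives 21 March, one day before first stimulation, so a genuine on-treatment event is not treatment-emergent by onset. The cause is that the imputation and the definition use different anchor dates.

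**Effect on the comparison.** Let p1 and p2 be the true double-blind proportions of subjects with an event, and let a fraction q of each arm gain a run-in event independently of the rest. Each proportion becomes p + q(1 − p), and the difference becomes (p1 − p2)(1 − q). For small q this is almost unchanged, while both absolute rates rise and their ratio moves towards 1.

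**The case against.** The strongest reply is that the rule is deliberately conservative for safety and will seldom matter. An event must start in a four-week window, lack its onset day, have a stop date good enough to place it before treatment, and share the month or year of treatment start. The adverse event row of Table 2 is ticked from V2, so run-in events can be recorded soon after they occur. Section 8.1 requires imputed values to be flagged and section 8.5.2 provides listings, so an impossible order would be visible. Section 7.5.2 also says that imputation is done where appropriate. Most of this stands as a limit on size. It does not remove the fault: no stop-date criterion is given, and the algorithm that follows is worded as mandatory.

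A reader might infer three stronger things that the SAP does not support.

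- **That every such event becomes treatment-emergent.** This needs first stimulation no later than the imputed date, and the SAP does not fix the day of first use.
- **That half of all run-in events lacking a day are reclassified.** The 52% counts onset days without allowing for resolution before treatment. Onsets nearest randomization are the likeliest to share its month and the least likely to have ended. Weighting onset–stop pairs gives about 38%.
- **That the active–sham safety comparison is materially biased.** No between-arm test of adverse events is specified, randomization should add such events about equally to both arms, and the device-related tables rest on the recorded causal assessment. Section 8.5.2 also does not restrict its tables to treatment-emergent events, so the main route to harm is assignment to the double-blind phase.

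**Conclusion.** The concern holds in a limited form. Followed as written, the rules can give a run-in event with a known pre-treatment stop date an onset after its resolution, and so place it in the double-blind tables. Treatment-emergent status follows as well only if first stimulation is on the randomization day.

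Under evenly spread dates, a known pre-treatment stop date and same-day first use, the share affected is about 38–52% of such run-in events lacking only the day and about 95–96% of those lacking month and day. These are shares of a number that the SAP does not give and that is probably small. The harm is misdated records and somewhat inflated absolute double-blind rates, with little expected effect on the risk difference and none on efficacy. The correction is cheap enough to make before unblinding.

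**What to change.** Make two changes to section 7.5.2 together.

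1. Add to start-date rules 1 and 2: *unless the event's full or partial stop date shows that it ended before first stimulation; in that case the imputed onset is no later than the stop date, the event is not treatment-emergent, and it is not counted in the double-blind table.*
2. Use the date of first stimulation as the anchor in both rules, in place of the earlier of two dates. Imputation and definition then agree, and partial-date events not shown to have ended before treatment keep treatment-emergent status when first use follows randomization.

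The second change should not be made alone: without the stop-date condition, run-in events with matching partial dates would become treatment-emergent whatever the lag to first use. With both, the enumerated events have an onset no later than their stop date, which precedes first stimulation, so none is misdated or misclassified. The conservative default remains wherever the stop date is unknown or later.

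The cost is an added sentence and a changed anchor date in the SAP, with the matching condition in the adverse event derivation. No new data are needed.

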#### **AE/ADE Counting Rules:**

- A subject with more than one different adverse event in a particular system organ class (SOC) will be counted only once in the total of subjects experiencing adverse events in that particular SOC.
- A subject having experienced the same event (AE preferred term) more than once during the study will be counted only once in the number of subjects with that event.
- If an event changes in intensity or in seriousness during the study, a subject will be counted only once with the worst grade and seriousness respectively.
- If the causal relationship to the study device is assessed differently, a subject will be counted only once by considering the “Worst” documented degree of relationship.

Frequency and percentage of subjects experiencing a specific adverse event will be tabulated by system organ class, preferred term, and treatment group for each study phase (i.e., double-blind randomized period, open-label period). Summary tables and subject data listings will be provided for adverse events by maximum intensity, device-related adverse events, serious adverse events, adverse events causing discontinuation of the device or participation in the study, and deaths.

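### Partial adverse event onset dates are anchored on randomization although treatment-emergence starts at first stimulation, and the SAP does not say how such events are assigned to a study phase

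*SAP*

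**What the plan says.** Section 7.5.2 of the SAP gives the definition: "An adverse event is considered treatment-emergent if the date of onset is on or after the date of first stimulation in the randomized period", or if the event worsens during the randomized or open-label period. For partial onset dates it says that "a complete date will be estimated by the following algorithm in order to determine treatment emergent", and gives two rules.

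- Rule 1, month and day missing. Year different from that of treatment start: "If the two years are not the same, then January 1 will be used". Same year: "then the earlier of the date of randomization and the date of first usage of the device will be used".
- Rule 2, day missing. Where the month and year are those of treatment start, the onset is the closest date, "being either on or after) the earlier of the date of randomization and the first date of usage of the device". Otherwise: "If the two did not occur in the same month and year, then 1 will be used for the day".

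Neither rule refers to the date on which the open-label device is issued. The counting rules in section 8.5.2 tabulate events by system organ class, preferred term and "treatment group for each study phase (i.e., double-blind randomized period, open-label period". Section 3.1 has sham subjects change to the active device after the 12-week randomized period, and section 5.3 analyzes safety by the treatment actually received.

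**The concern.** The definition and the imputation use different anchors, although the imputation exists to apply the definition. An event that the rules try to place at the start of treatment can be placed just before it, and so lose treatment-emergent status.

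The second issue is phase. The SAP tabulates adverse events by phase and gives no onset date for a partially dated event other than the imputed one. A programmer may well use that date to choose the phase. The rules tend to give early dates, so the error runs one way: open-label events move back into the double-blind period. In the active arm the event stays on the active device. In the sham arm an event on active stimulation would be shown under sham, in the randomized comparison.

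**Working it through.** The SAP gives no figure to reproduce, so the check applies its rules literally.

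**Inputs from the SAP.** R is the randomization date, F the date of first stimulation (taken to be the date of first device use) and O the open-label start. Section 3.2 provides the device serial number together with the randomization number, so F cannot precede R, and the earlier of the two is always R. Table 2 puts randomization and device training at the same visit (V2), but nothing fixes first use to that day. Open label runs from about day 84 to day 252.

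**Rules as formulas.**
- Rule 1: imputed onset = R if the year equals that of treatment start, otherwise 1 January.
- Rule 2: imputed onset = the later of R and the first of the month if the month and year match treatment start, otherwise the first of the month.
- An event is treatment-emergent by onset only if imputed onset ≥ F.

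Under rule 1 a matching date gives R, and R ≥ F only if R = F. Under rule 2 the flag also survives if F is the first of the month and R falls in the month before. Non-matching dates after treatment start always fall after F, so none of them is lost.

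**Examples.** In the first four rows R = 1 March 2016, F = 2 March and O = 24 May. In the last row R = 1 December 2015 and O = 23 February 2016 (30 + 31 + 23 = 84 days).

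| True onset | Recorded as | Imputed | Effect |
|---|---|---|---|
| 20 March 2016 | March 2016 | 1 March | before F, flag lost |
| 1 Sept 2016 | 2016 | 1 March | before F and before O |
| 28 May 2016 | May 2016 | 1 May | before O |
| 10 Sept 2016 | Sept 2016 | 1 Sept | no error |
| 1 June 2016 | 2016 | 1 January 2016 | before O |

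**Frequency.** Assumptions not in the SAP: 365 equally likely randomization dates, every onset day from F to day 252 equally likely, O at day 84, and a lag F − R of 0, 1 or 3 days. The percentages are shares of partially dated onsets, not of all events.

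*Treatment-emergent flag lost:*

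| Lag | Year-only | Month and year |
|---|---|---|
| 0 days | 0% | 0% |
| 1 day | 60,354/91,980 = 65.6% | 5,373/91,980 = 5.8% |
| 3 days | 60,125/91,250 = 65.9% | 5,373/91,250 = 5.9% |

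At lags of 1 and 3 days, every year-only onset in the treatment-start year is lost. Of the 5,738 month-and-year onsets in the start month, all are lost except 5,738 − 5,373 = 365, where F is the first of the month. With F as the anchor, the loss is 0% at every lag.

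*Open-label onsets dated before O (lag 0):*
- Year-only: 33,012/61,320 = 53.8% go to the randomization date. A further 13,944/61,320 = 22.7% go to a 1 January before the switch. Together this is 46,956/61,320 = 76.6%.
- Month and year: none go to the randomization date, and 5,041/61,320 = 8.2% move through the first-of-month rule.

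The totals of 76.6% and 8.2% are the same at lags of 1 and 3 days, and anchoring on F does not reduce them.

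A side effect: if R and F straddle New Year, rule 1 returns a date outside the year that was reported. Anchoring on F removes this too.

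**The case against.** Much of the case on the other side stands.

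- **The reach is limited.** A reader might infer that partial dates in general go to the randomization date. They do so only where the year, or month and year, match treatment start.
- **The lag is an assumption.** Randomization and training share a visit, and with same-day first use no flag is lost. The requirement in section 5.1 for a verified treatment after training does not show that first use falls on a later date.
- **Nothing is dropped.** A reader might infer that these events vanish from the safety report. Sections 7.5.2 and 8.5.2 keep all events in the tabulations whatever the state of their dates, and section 8.5.2 names no separate treatment-emergent table. An event that later worsens is treatment-emergent anyway.
- **Phase by imputed date is an inference.** The stated purpose of the algorithm is treatment-emergent status. Partial dates may be imputed where appropriate, and events are collected at every visit or call from V2, so the reporting visit can often bound the phase. A reader might conclude that the SAP moves active-device events into the sham column. It does not say so. It leaves the assignment open and supplies only one date that could serve.
- **A one-sided remedy would do harm.** Sending ambiguous events to open label for sham-arm subjects only would take genuine sham-phase events out of the blinded comparison while leaving matching active-arm events in.

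The mismatch of anchors within section 7.5.2 and the lack of a phase rule for partial dates remain.

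**Conclusion.** The point holds and is minor. The definition and the imputation disagree. Wherever first stimulation falls after the randomization day, an onset known only to the treatment-start year is classed as not treatment-emergent. The same holds for one known only to the treatment-start month, unless first use is on the first of that month. With same-day first use the disagreement has no effect.

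The phase problem is conditional: it arises only if the imputed date is used for the by-phase tables. In that case about 77% of year-only and 8% of month-and-year open-label onsets would fall before the open-label device, given uniform dates and a switch at day 84. Attribution to the wrong device is confined to sham-arm subjects. The SAP does not give the number of partial dates. It is probably small given the frequent contacts, and year-only dates should be the rarer kind. The documents do not support a claim that the reported safety comparison will be materially biased.

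**What to change.** 1. In both onset rules of section 7.5.2, replace the earlier-of-two-dates anchor with the date of first stimulation. The rules then agree with the definition at any lag.
2. Add a sentence to section 8.5.2 on the phase of partially dated events. Use one rule, identical in both arms, based on the visit or call at which the event was first reported and on its stop date. Flag events whose phase stays ambiguous.

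The second change is needed because the first does not touch the phase shift. The cost is a few sentences and some programming, with no new data. A few more partially dated events may count as treatment-emergent, including run-in events dated only to the start month or year. That already happens under the present rule when first use is on the randomization day.

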### **7.5.3 Concomitant Medications/Treatments**

Verbatim terms will be coded by Sponsor and assigned an Anatomic-Therapeutic-Chemical (ATC) term using the World Health Organization Data Dictionary Extended (WHO-DDE), version 2015Sep.

